## **5.7 Calculation of eGFR**

Calculation is based on locally measured creatinine from a blood sample. At the time of screening the local eGFR will be used for evaluation of inclusions criteria no. 5 only.

[figure not shown]
Information in the eCRF is based on the creatinine measurement method in the local laboratory. The central calculation of eGFR will be made with CKD-EPI equation. The estimation will be made centrally in the eCRF after entry of creatinine data by the investigators.

CKD-EPI equation:  $GFR = 141 \times \min(Scr/\kappa, 1)^\alpha \times \max(Scr/\kappa, 1)^{-1.209} \times 0.993^{Age} \times 1.018$  [if female]  $\times 1.159$  [if black]. Where Scr is serum creatinine (mg/dL),  $\kappa$  is 0.7 for females and 0.9 for males,  $\alpha$  is  $-0.329$  for females and  $-0.411$  for males, min indicates the minimum of Scr/ $\kappa$  or 1, and max indicates the maximum of Scr/ $\kappa$  or 1.

The information in the eCRF on eGFR will be used as safety measures throughout the study.

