## 6.3 Intervention group (group B) / High-risk population

Randomized, double-blind, placebo-controlled, multicenter study in the high-risk population based on urinary proteomic risk pattern assessment. It is estimated that 15% of the total population (approx. 300 patients) will show a high-risk pattern.

Patients will be invited to participate if the urinary proteomic pattern after the screening visit is showing a high-risk pattern, and if at least two of the three samples from the "run-in"-period show normoalbuminuria (UACR <30 mg/g) analyzed at the central laboratory.

Patients in the intervention study will be randomized (1:1) to spironolactone 25 mg daily or matching placebo in addition to standard treatment according to the investigators discretion. Patients will be stratified in the two treatment arms (1:1) based on whether or not the patients is treated with RAS blocking agents at the time of entry (Screening).

Patients are seen according to Table 1, with a study visit every 13th weeks. Patients must be treated by the investigator for standard diabetes care according to local guidelines. Dependent on time of baseline the patients will be treated for at least 104 weeks with measurements of UACR, BP, medication, and locally measured creatinine, sodium, potassium, and lipids (cholesterol, HDL, LDL, triglycerides). HbA1c will be measured in DCCT-aligned quality control programs or IFCC. At screening and in the duration of the study, the medical history regarding vascular events, current retinopathy status (by history) and information on laser treatment, as well as adverse events (see section 13.3), including hospital admissions, are registered.

Potassium levels will be measured locally as indicated in table 1.

Secondary endpoints and adverse events (see section 13.3) will be registered at the visits every 13 weeks.

After the last study visit patients will continue in the observational long-term follow-up in accordance with section 6.4.

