## **10.8 Blood samples**

Clinical chemistry has to be performed according to table 1 with measurement of creatinine (traceable standardized method), sodium, and potassium at every visit. HbA1c (DCCT-aligned method or IFCC) has to be measured at Screening and every periodic visit in both groups. Lipids (cholesterol, HDL, LDL, and triglycerides) have to be measured at least every year in all patients.

All blood samples are to be analysed locally.

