#### **14.6 Criteria for discontinuation**

A participant must be discontinued in the IMP treatment if any of the following is present:

- Female patients in the intervention study who become pregnant, intend to become pregnant or do not use adequate birth control (according to inclusion criteria 7, in section 7.1).
- Experience of research-related injury or unacceptable side effects to the study medication.
- Safety considerations assessed by the investigator
- Treatment with Lithium (ATC: N05AN).
- Treatment with potassium sparing diuretics (ATC: C03D, C03E).
- Confirmed eGFR below 15 ml/min/1.73 m^2.
- Confirmed elevated liver enzyme (ASAT and/or ALT) 3 times above normal range.

Discontinued patients will be offered tests corresponding to the final study visit. Data on all patients will be included in the study and will be used in safety analysis.

After discontinuation of study medication in the randomized population, observation should continue with visits as planned in the observational group (if the patient accepts), or if that is not possible/acceptable, evaluation of vital status and development of endpoints should be evaluated through registries, information of hospitals and GPs, or interviews with the patient as appropriate and possible in order to monitor development of endpoints in all included patients as thoroughly as possible, provided that the patient agrees.

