6.1.2 Secondary outcome

- A. Comparison of composite fatal and non-fatal cardiovascular outcome (MI, stroke, CABG, PTCA, hospitalization for heart failure and CVD) and all-cause mortality during the study.
- B. Comparison of incidence of retinopathy and frequency of laser treatment. Data collected from self-reported AEs.
- C. In addition to the categorical analysis of UACR, an analysis will be performed with changes in geometric mean of UACR throughout the study period in all patients by assessing the slope of albuminuria changes and absolute changes from inclusion to end of trial.
- D. Development of microalbuminuria (UACR >30 mg/g) in at least one morning void urine sample will be used as a secondary outcome instead of confirmed microalbuminuria.
- E. Development of macroalbuminuria (UACR >300 mg/g) in 2 out 3 first morning void urine samples).
- F. For patients with eGFR ≥ 60 ml/ min/ 1.73 m² at baseline, development of eGFR <60 ml/min/1.73m².
- G. Development of CKD stage 4 (eGFR <30 ml/min/1.73m²).
- H. Change in eGFR (slope) from baseline and from three-month post-baseline to end of study.
- I. Change in eGFR (40 % reduction) from baseline and from three-month post-baseline to end of study.
- J. Safety: Adverse Events and Serious Adverse Events. Adverse Events leading to death or discontinuation of study medication and/or withdrawal.
- K. Event of hyperkalaemia with potassium level in plasma ≥ 5.5 mmol and/or ≥ 5.8 mmol in serum at any time point.

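### Outcome F (eGFR below 60) counts one unconfirmed creatinine, and high-risk patients are tested about four times as often as low-risk patients, which tilts the CKD273 comparison

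*SAP*

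**What the plan says.** - **Definition.** SAP 6.1.2 F, also listed in protocol 5.5.1 and 5.5.2, applies to patients with eGFR of at least 60 and reads "at baseline, development of eGFR <60 ml/min/1.73m". It asks for no repeat value, no persistence and no minimum fall. The SAP does not state that one value suffices; it is silent.
- **Analysis.** SAP 6.3.1.2 and 6.3.2.2 put every secondary outcome except C, H and J into Cox models, in the observational cohort and in the randomised comparison. Without a confirmation rule, the first value below 60 is the event.
- **Measurement.** Protocol 5.7: "Calculation is based on locally measured creatinine from a blood sample". The CKD-EPI value is then computed centrally in the eCRF. Protocol 10.8 asks for "measurement of creatinine (traceable standardized method), sodium, and potassium at every visit".
- **Schedule.** For the high-risk group, protocol 6.3 says "Patients are seen according to Table 1, with a study visit every 13th weeks", and Table 1 adds week 2. Protocol 6.2 gives the low-risk group yearly measurements.
- **Existing correction.** SAP 6.3.1.3 recognises that the high-risk stratum is measured more often. It moves a primary event found between annual visits to the next annual visit. It names the primary endpoint only.
- **Confirmation elsewhere.** The primary outcome and macroalbuminuria need two of three voids. The criterion for stopping study medication in protocol 14.6 is "Confirmed eGFR below 15 ml/min/1.73 m", with confirmation written in.

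**The concern.** A patient with a true eGFR a little above 60 will sometimes read below 60 by chance, and each further test is another opportunity. Where one low reading is enough, the event rate depends on how often the patient is tested as well as on kidney function. The two risk strata are tested at intervals of 13 and 52 weeks, a ratio of 4. In the high- versus low-risk comparison the extra chance events therefore fall mostly in the high-risk stratum, the direction that the trial hopes to show. An apparent ability of CKD273 to predict a fall below 60 could come partly from the visit calendar.

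In the randomised comparison both arms are tested alike. Chance events there favour neither arm, but they blur the contrast.

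**Working it through.** The documents give no figure for F to reproduce, and no creatinine variability, eGFR slope or baseline eGFR distribution. Those three inputs are assumptions below; the visit schedule is from the protocol.

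**1. Number of tests.** Over 130 weeks a high-risk patient has week 2 plus weeks 13 to 130, so 1 + 10 = 11. A low-risk patient has weeks 52 and 104 plus the final visit, so 3. Over 156 weeks the counts are 13 and 3. The maximum in Table 1 is 1 + 17 + 1 = 19 against 4 + 1 = 5.

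**2. A stable patient.** With lognormal error, the chance of one reading below 60 is p = Φ(ln(60 / true eGFR) / CV). The chance of at least one in m tests is 1 − (1 − p)^m. For a true eGFR of 65 and CV 5%, p = Φ(−0.0800 / 0.05) = Φ(−1.60) = 0.055. Three tests give 1 − 0.945³ = 16%, and eleven give 1 − 0.945¹¹ = 46%.

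| True eGFR | Tests | CV 3% | CV 5% | CV 8% | CV 10% |
|---|---|---|---|---|---|
| 65 | 3 | 1% | 16% | 40% | 51% |
| 65 | 11 | 4% | 46% | 85% | 93% |
| 70 | 3 | <0.1% | 0.3% | 8% | 17% |
| 70 | 11 | <0.1% | 1% | 26% | 50% |

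**3. A whole cohort.** The same simulated patients were put on both schedules. Assumptions: true eGFR normal with mean 85 and SD 15 (SD 17 in the last row), entry above 45, measured baseline at least 60.

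| Weeks | Slope per year | CV | F, 13-weekly | F, annual + final | Ratio |
|---|---|---|---|---|---|
| 130 | −1 | 5% | 6.6% | 4.6% | 1.43 |
| 130 | −1 | 8% | 10.9% | 6.7% | 1.63 |
| 156 | −1 | 5% | 7.4% | 4.9% | 1.51 |
| 156 | −1 | 8% | 12.4% | 7.1% | 1.75 |
| 130 | −2 | 5% | 10.8% | 8.7% | 1.24 |

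Across CV 3–10%, slope −1 or −2 and 130–156 weeks the ratio runs from about 1.15 (CV 3%, slope −2, 130 weeks) to about 1.8 (CV 10%, slope −1, 156 weeks). The strata do not differ in true kidney function in any of these runs.

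**4. Would confirmation alone remove the imbalance?** No. In the last row, requiring two consecutive values below 60 lowers F from 10.8% to 6.3% on the 13-weekly schedule and from 8.7% to 4.6% on the annual one. The ratio is still 6.3 / 4.6 = 1.37. Moving the event date to the next annual visit would not do it either, because every extra event would still be counted. The values used must be the same in both strata.

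**5. Spironolactone versus placebo.** A treatment that halves a mean slope of −2 (SD 1.5) was simulated.

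| CV | Rule | Hazard ratio | Events | Absolute log HR × √(event proportion) |
|---|---|---|---|---|
| 8% | single value | 0.77 | 16.4% | 0.261 × 0.405 = 0.106 |
| 8% | two consecutive | 0.70 | 7.7% | 0.357 × 0.277 = 0.099 |
| 5% | single value | 0.70 | 11.2% | 0.357 × 0.335 = 0.119 |
| 5% | two consecutive | 0.62 | 6.6% | 0.478 × 0.257 = 0.123 |

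The single-value rule pulls the hazard ratio towards 1 but finds more events, so the signal is about equal under the two rules.

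**The case against.** The strongest points on the other side are these.

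- **Single-value outcomes are not unusual in this SAP.** A reader might infer that only the renal-function outcomes lack confirmation. That is not so: D needs one morning void above 30 mg/g, and K needs one raised potassium. The confirmed eGFR in protocol 14.6 is a rule for stopping medication, not an outcome. This stands, and the point does not rest on inconsistency.
- **F is one of several secondary outcomes.** SAP 4.1 gives secondary p-values only if the primary analysis succeeds, and outcome H uses repeated eGFR values in a mixed model. This limits the harm, but a hazard ratio and interval for F would still be reported.
- **SAP 6.4 reruns the high- versus low-risk Cox model on annual samples.** It does so without the spironolactone arm and does not name the outcome; the paragraph before it names the primary outcome. It cannot be relied on to cover F.
- **Confirmation has a price.** It cuts F events by roughly half, cannot confirm a fall first seen at the last visit, and loses patients who leave after one low value. This stands, and is why confirmation is proposed below as a sensitivity analysis and not as the main definition.

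A reader might also extend the noise argument to "Development of CKD stage 4 (eGFR <30 ml/min/1.73m" and to "Change in eGFR (40 % reduction) from baseline and from three-month post-baseline to end of study". The arithmetic does not support that. At CV 10% and 11 tests, a stable patient at 46 reads below 30 with a chance of about 0.01%, and a stable patient shows a 40% fall with a chance of at most about 0.2%.

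**Conclusion.** The point holds for F. As written, the comparison of F between risk strata is biased towards the CKD273 hypothesis by the visit schedule alone. The excess is about 1.15 to 1.8 times as many events; at slope −1 and 130 weeks it is 2.0 percentage points at CV 5% (6.6 − 4.6) and 4.2 at CV 8% (10.9 − 6.7). The direction follows from the schedule and the missing rule. The size rests on the assumed CV, slope and baseline distribution.

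For spironolactone versus placebo the effect is mainly dilution. Two stronger readings are tempting and not supported:

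- **That most F events are noise.** Over 130 weeks of 13-weekly testing (CV 3–10%, slopes −1 to −3), true eGFR is still at least 60 on the event date in 53–90% of events, but still at least 60 at week 130 in 15–77%. The answer turns on the definition of noise and on inputs that the documents do not give.
- **That a definite diluted hazard ratio can be stated.** Treating every unconfirmed event as untouched by treatment overstates the dilution, because a treatment that slows decline also reduces chance dips below 60.

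**What to change.** 1. **High versus low risk.** In SAP 6.3.1.2, state that F is analysed on annual and final-visit creatinine values only, in both strata.
2. **Spironolactone versus placebo.** In SAP 6.3.2, add a sensitivity analysis in which F requires a value below 60 at two consecutive scheduled visits, dated at the first. The week-2 value should not be able to start an event; outcomes H and I already have a version that starts three months after baseline, while F has none. Report this beside the single-value result.

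The cost is SAP wording and reprogramming on creatinine values already in the eCRF. The first change gives up the high-risk values between annual visits. The second has fewer events, and a fall first seen at the last visit cannot be confirmed. G and I need no change on grounds of measurement noise.

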### 5.5 Secondary endpoints

#### 5.5.1 In the total population:

In the following paragraphs patients in the intervention group, (group B) and observation group (group A) will be compared.

- Comparison of composite fatal and non-fatal cardiovascular outcome (MI, stroke, CABG, PTCA, hospitalization for heart failure and CVD), and all-cause mortality during the study.

- Comparison of incidence of retinopathy and frequency of laser treatment. Data collected from self-reported AEs
- In addition to the categorical analysis of urinary albumin excretion, an analysis will be performed with changes in geometric mean albuminuria throughout the study period in all patients by assessing the slope of albuminuria changes and absolute changes from inclusion to end of trial
- Development of microalbuminuria (UACR >30 mg/g) in at least one morning void urine sample will be used as a secondary outcome instead of confirmed microalbuminuria
- Development of macroalbuminuria (UACR >300 mg/g in 2 out 3 first morning void urine samples)
- For patients with eGFR  $\geq 60$  at baseline, development of eGFR <60 ml/min/1.73m^2.
- Change in eGFR (slope and absolute from baseline and from 3 month post-baseline to end of study)

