## 6.2 Observation group (group A) / Low-risk population

It is expected that 85% of the total population (approx. 1700 patients) will show a low-risk pattern. Patients should be followed by the investigator in routine clinics or seen once yearly, for standard diabetes care according to local guidelines. Annual measurements of UACR, BP, medication, and locally measured creatinine, sodium, potassium, and lipids (cholesterol, HDL, LDL, triglycerides) will be performed. HbA1c will be measured in DCCT-aligned quality control programs or IFCC. During the study, the medical history regarding vascular events, current retinopathy status (by history) and information on laser treatment, as well significant medical events (see section 10.14.), including hospital admissions, are registered.

Secondary endpoints and significant medical events will be registered at the annual visits.

After the last study visit, patients will continue in the observational long-term follow-up in accordance with section 6.4.

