**Table 1: Frequency of study visits at each participating center**

Assessment procedures									
Visit	Total Population			Intervention Group (Group B, high-risk population)				Observational Group (Group A, low-risk population)	
	Screening	Run in - period	Baseline	Visit 1	Periodic study visits		End of study/ Early Termination Visit	Periodic study visits	End of study/ Early Termination Visit
Study week	Week -12 to -4	Week -11 to -2	Day 0	Week 2 (± 3 days)	Week 13, 26, 39, 52, 65, 78, 91, 104, 117, 130, 143, 156, 169, 182, 195, 208 and 221 (± 14 days)	Week 52, 104, 156 and 208 (± 14 days)	Planned end (July to September 2018) or early Termination	Week 52, 104, 156 and 208 (± 14 days)	Planned end (July to September 2018) or early Termination
Informed consent	x		x 						
Inclusion/ Exclusion criteria	x		x 						
Medical history			x						
Tobacco/alcohol usage			x						
Concomitant medication	X 		x	x	x		x	x	x
Physical examination 			x		x		x	x	x
Height	X								
Weight	x					x	x	x	x
Vital signs (BP/Heart rate) 	x		x		x		x	x	x
Study medication			x		x		x		
Local clinical laboratory examinations clinical chemis- try (blood sam- ples)	Creatinine, sodium, potassium,	x	x	x	x		x	x	x
	HbA1c	x		x 	x		x	x	x
	Cholesterol, LDL, HDL, Triglyceride			x		x	x	x	x
3 consecutive first morning void urine samples for albuminuria assessment	Central Analyses		x 		x		x	x	x
	Central Storage 		x			x	x	x	x
Urine sample for proteomic analysis	x								
Biobank sampling (after informed consent)			x				x		x
Randomization (applicable for group B)			(R)						
Adverse Events				x	x		x		
Significant medical event								x	x
Urine dipstick analysis 	x	x			x		x	x	x
Pregnancy test 	x						x		
Final assessment							x		x

1) Informed consent for the biobank participation.

2) Only the inclusion criteria regarding UACR and exclusion criteria regarding BP will be evaluated.

- 3) The physical examination performed at the Baseline visit will serve as the baseline for clinical assessment. At baseline the examination will include: General appearance, heart, lungs, abdominal, lymph nodes and extremities. At all other visit, a symptom-directed physical exam will be performed. Any new clinically significant physical exam findings after the Baseline/Randomization Visit will be recorded as adverse events.

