6.3.1.2 Analysis of secondary endpoints

Based on a 2x2 table included the primary endpoint (event/ event free) vs. risk stratification ("high"/- "low"-risk) we will calculate sensitivity, specificity and numbers need to screen for CKD273 and tested for significance using Chi-square test. In a logistic model we will added value using AUC and ROC with comparison between "high"- and "low"-risk vs. event and event-free for both primary endpoint. The logistic models will be performed both unadjusted and adjusted for age, gender, HbA_{1c}, systolic blood pressure, retinopathy, eGFR and UACR at baseline.

For the Cox-regression model a model, including adjustment for age, gender, Hba1c, systolic blood pressure, retinopathy eGFR and UACR at baseline will be comprised for secondary endpoints (see section 6.1.1 and 6.1.2, excluding 6.1.2 C, H and J).

For further clarification of the added value for discrimination, the rIDI will be calculated based on all above described Cox-regressions models with a significant HR for CKD273 in the unadjusted model for each endpoint.

To evaluate changes in UACR and eGFR over time (outcome measurement C and H in section 6.2.1) a linear mix model will be applied with adjustment for eGFR and UACR at baseline.

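### The three-month-anchored 40% eGFR reduction (outcome I) has no reference value in the low-risk group, yet the SAP includes it in the high- versus low-risk Cox models

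*SAP*

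**What the plan says.** **Outcomes.** SAP 6.1.2 lists outcome H as "Change in eGFR (slope) from baseline and from three-month post-baseline to end of study" and outcome I as "Change in eGFR (40 % reduction) from baseline and from three-month post-baseline to end of study". Each therefore has a baseline version and a three-month version.

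**Where the three-month start comes from.** Protocol 5.5.1 lists eGFR change, as slope and as absolute change, from both starting points. It places them under the total population, where "patients in the intervention group, (group B) and observation group (group A) will be compared". The high- versus low-risk use is therefore explicit in the protocol.

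**Analyses.** In the observational cohort, SAP 6.3.1.2 applies adjusted Cox models to the endpoints ("see section 6.1.1 and 6.1.2, excluding 6.1.2 C, H and J"), so I stays in. H goes to a linear mixed model adjusted for baseline eGFR and UACR. SAP 4.3.2 defines this cohort by a valid proteomic score and baseline data, so the low-risk patients belong to it.

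**Schedule.** Protocol 6.2 gives the low-risk group "Annual measurements of UACR, BP, medication, and locally measured creatinine, sodium, potassium, and lipids". Table 1 agrees: its low-risk periodic visits fall at weeks 52, 104, 156 and 208, followed by the final visit. High-risk patients are seen at week 2 and then every 13 weeks up to week 221. Protocol 10.8 ties creatinine to these visits.

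**Handling.** SAP 6.2 rules out any assumption or method for missing values. SAP 6.3.1.3 recognises that the two strata are sampled at different frequencies, but its correction is for the primary endpoint.

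**The concern.** A 40% fall from a three-month value needs a three-month value. The low-risk schedule does not supply one, and the SAP names no substitute.

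Run literally, the three-month Cox model for I keeps only the high-risk stratum, so no high- versus low-risk hazard ratio can be estimated. The rIDI step in SAP 6.3.1.2 needs a significant unadjusted hazard ratio for CKD273, so it fails with it. The analyst would then have to drop the analysis or choose another reference after seeing the data, which is a choice the SAP should already have made.

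Two lesser problems follow from the same schedule. The three-month slope covers a different stretch of follow-up in each stratum. And even from a baseline reference, a threshold event such as a 40% fall is looked for more often in high-risk patients, which can raise their apparent event rate and bring their event dates forward.

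**Working it through.** The plan gives no figure of its own on this point, so the check is a count of scheduled creatinine values.

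**Inputs.** Low-risk visits: baseline, weeks 52, 104, 156, 208 and final (Protocol 6.2, Table 1). High-risk visits: baseline, week 2, weeks 13 to 221 in steps of 13, and final (Table 1). Creatinine at each (Protocol 10.8). Follow-up of 104 to 230 weeks (Protocol 6.1). Cohort of 1,811 (SAP 2.2 and 2.3.1). Planned low-risk share of 85% (Protocol 6.2).

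**Step 1: is there a three-month value?**

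| Scheduled creatinine values | Low risk | High risk |
|---|---|---|
| Strictly between baseline and week 52 | 0 | 4 (weeks 2, 13, 26, 39) |
| Within week 13 ± 2 weeks | 0 | 1 |

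**Step 2: outcome I.** The event occurs at the first time t with eGFR(t) ≤ 0.60 × eGFR(reference).
- Reference = baseline: defined in both strata.
- Reference = three months: defined in the high-risk stratum at week 13, and undefined under the schedule for every low-risk patient.

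The absolute change from three months in Protocol 5.5.1 fails for the same reason.

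**Step 3: outcome H.** A mixed-model slope needs no observation at month 3 itself. Scheduled values from week 13 onward, counting the final visit as the last one:

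| Follow-up (weeks) | Low risk (first at week 52) | High risk (first at week 13) | Ratio |
|---|---|---|---|
| 104 | 2 | 8 | 8 / 2 = 4.0 |
| 156 | 3 | 12 | 12 / 3 = 4.0 |
| 208 | 4 | 16 | 16 / 4 = 4.0 |
| 230 | 5 | 18 | 18 / 5 = 3.6 |

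The slope can be fitted in low-risk patients, but its data start 52 − 13 = 39 weeks later. The two windows estimate the same quantity only if eGFR changes linearly across the first year, which low-risk data after three months cannot check.

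**Step 4: chances of detecting a 40% fall.** The same table shows the imbalance for I with a baseline reference: 8 looks against 2 by week 104, not counting the extra high-risk value at week 2.

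**Step 5: size of the affected stratum.** 0.85 × 1,811 = 1,539 low-risk patients at the planned share. The result of Step 2 does not depend on this share, because no low-risk patient has a scheduled three-month value.

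**The case against.** **The baseline versions survive.** H and I are both also defined from baseline, and those versions can be computed in each stratum. A reader might infer that the eGFR outcomes as a whole fail in the low-risk group. They do not: the failure is confined to the three-month version of I and the protocol's absolute change from three months. For H the problem is unequal windows.

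**A 39-week shift in the reference for I is not planned.** A reader might infer that low-risk patients would be referenced to week 52. The SAP says nothing of the kind, and SAP 6.2 excludes methods for missing data. The shift would arise only through an unplanned substitution. For I, the documented defect is the absence of any usable rule.

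**Early drug effect.** It is tempting to add that the week 13 value in half the high-risk stratum already reflects spironolactone. Neither document describes an early effect of spironolactone on eGFR. If there were one, a later anchor would tend to remove it and a baseline anchor would include it. It is therefore no argument for the change proposed here.

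**Visit asymmetry is partly recognised elsewhere.** SAP 6.4 plans Cox models without the active arm, on all data and on annual samples only. It names no endpoint and supplies no three-month value, so it does not close the gap.

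**Stray values exist.** Unscheduled visits (Protocol 10.19) and early termination visits could yield a low-risk creatinine near month 3, but not systematically. Conversely, high-risk patients who stop study medication before week 13 move to the observational visit plan (Protocol 14.6) and may also lack the anchor.

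**Limited stakes.** These are secondary outcomes, and under SAP 4.1 their p-values are calculated only if the primary analysis gives p < 0.05. This limits the importance of the point, but one specified comparison still cannot be carried out.

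**Conclusion.** The point holds in a limited form. The three-month-anchored 40% reduction cannot be computed in low-risk patients from scheduled data, yet SAP 6.3.1.2 leaves it in the high- versus low-risk Cox models. The three-month slope can be fitted but compares week 52 onward with week 13 onward. The baseline-anchored 40% reduction is computable, but with about four times as many scheduled looks in the high-risk stratum and no stated correction for this outcome.

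This rests on the schedule as written and on a month-3 value being the week 13 visit. Table 1 is broken in the extracted text, but Protocol 6.2 independently confirms the annual low-risk creatinine. The primary endpoint, the randomised comparison and the baseline-anchored slope are not affected.

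**What to change.** 1. In SAP 6.3.1.2, state that the three-month versions of H and I are not analysed for high versus low risk. Keep them for active versus placebo under SAP 6.3.2.2, where week 13 supplies the reference.
2. Record this as a change from Protocol 5.5.1, which lists the three-month eGFR change for the group A versus group B comparison.
3. For high versus low risk, analyse I from the baseline reference, using only annual and final creatinine in both strata.
4. For high versus low risk, analyse H as the slope from baseline using all available data. Thinning to annual visits is unnecessary here, since a mixed model accepts unequally spaced measurements.

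**Cost.** No new data are needed. The three-month version of a protocol-listed secondary endpoint is given up for the high- versus low-risk comparison. For I in that comparison, the interim high-risk values go unused: up to 17 − 4 = 13 of the 13-weekly visits, plus week 2. They remain available for the randomised comparison, for the slope and for safety.
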